4.1 Inclusion Criteria

- 101 Subject has provided informed consent prior to initiation of any study-specific activities/procedures
- 102 Male or female age ≥ 18 years at the time of informed consent
- 103 Histologically confirmed diagnosis of metastatic or recurrent SCCHN of the oral cavity, oropharynx, hypopharynx, or larynx. Disease must be unsuitable for curative surgical resection and must not be amenable to curative radiotherapy.
- 104 Disease must have progressed after treatment with a platinum-containing regimen and should be defined as one of the following:
- disease progression or recurrence between 3 to 6 months of prior curatively intended multimodal therapy (which includes platinum therapy) for locoregionally advanced SCCHN.

Note: This criterion is only applicable for subjects who have not had treatment in the recurrent/metastatic setting.

- disease progression or recurrence after prior platinum therapy in the recurrent or metastatic setting
- 105 Subject must be candidate for intralesional therapy administration defined as one or more of the following:
- at least 1 injectable cutaneous, subcutaneous, or nodal SCCHN tumor ≥ 10 mm in longest diameter
 - multiple injectable cutaneous, subcutaneous, or nodal SCCHN tumors that in aggregate have a longest diameter of ≥ 10 mm

Note: Mucosal surfaces of tumor lesions and visceral metastases should not be injected.

- 106 Subject must have radiographically measurable disease per RECIST v1.1 ([Eisenhauer et al, 2009](#)). Target lesions must not be chosen from a previously irradiated field unless there has been radiographically and/or pathologically documented tumor progression in that lesion prior to enrollment
- 107 ECOG performance status of 0 or 1

108 Adequate organ function determined prior to enrollment, defined as follows:

- Hematological
 - $ANC \geq 1.5 \times 10^9/L$
 - platelet count $\geq 100 \times 10^9/L$
 - hemoglobin ≥ 9 g/dL

Note: Subjects who have received transfusion of blood products (including platelets or red blood cells, or administration of colony stimulating factors [including G-CSF, GM-CSF, or recombinant erythropoietin) within 4 weeks prior to the first study treatment will be excluded.

- Renal

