Baseline evaluations will be used to prospectively identify all sites of disease present as close as possible to the enrollment and never greater than or equal to 28 days before the enrollment date. Sites of disease will be characterized as either target, non-target lesions or new lesions.

Baseline Documentation of Target Lesions:

Up to 10 target lesions with a maximum of 5 per organ (phase 1b) and up to 5 target lesions with a maximum of 2 per organ (phase 3) will be chosen to measure over the course of therapy. Pathological lymph nodes that are defined as measurable must meet the criterion of a short axis of ≥ 15 mm by CT scan in order to be identified as target lesions.

Target lesions should be selected on the basis of their size (lesions with longest diameter) and suitability for accurate repeated measurements by radiographic imaging. In situations where larger lesions cannot be accurately measured repeatedly (eg, near the diaphragm where respiratory changes may affect measurements), smaller lesions that meet criteria for measurability may be selected instead. Target lesions must not be chosen from a previously irradiated field unless there has been documented tumor progression in that field prior to enrollment. The distribution of the target lesions should be representative of the subject’s overall disease (eg, largest lesions per organ).

A sum of the diameters (longest for non-nodal lesions, short axis for nodal lesions) for all target lesions will be calculated and reported as the baseline sum diameters. The baseline sum of diameters will be used as reference by which to characterize the objective tumor response.

Baseline Documentation of Non-Target Lesions:

Any measurable lesions that were not chosen as target lesions and pathological lymph nodes with short axis ≥ 10 mm but < 15 mm, as well as non-measurable lesions should be identified as non-target lesions. Non-target lesions are evaluated at each timepoint but measurements are not required.

Documentation of New Lesions:

Any new lesion that appears during the course of study will be categorized as a new lesion. New lesions are evaluated at each timepoint but measurements are not required.

Follow-up Assessment of Tumor Lesions:

At each subsequent tumor assessment, the sum of diameters of target lesions will contribute to the total tumor burden.

Tumor Burden = sum of diameter of target lesions

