New lesions and non-target lesion measurements are not required and these lesions should be followed qualitatively.

For radiographically assessed non-nodal disease the convention will be used that if a lesion being measured decreases in size to ≤ 5 mm in diameter or if it is believed to be present and faintly seen but too small to measure, a value of 5 mm will be assigned. If the non-nodal lesion subsequently increases in size to greater than or equal to 5 mm in one dimension, its true size will be recorded. If it is in the opinion of the radiologist that the non-nodal lesion has likely disappeared, the measurement should be recorded as "0 mm". If a lymph node is nonpathological (< 10 mm), dimensions should be recorded as 5 mm.

Response Evaluation:

Evaluation of Objective Response:

The subject response will be assessed based on tumor burden (the sum of diameters of target lesions) and qualitative assessment of non-target lesions per the definitions in [Table 12](#). The overall response is derived from time-point response assessments as described in [Table 14](#). Treatment decisions based on initial progressive disease are described in [Table 13](#).

**Table 12. Definition of Measurable Tumor Response
(Baseline Target, Non-target, and New Lesions) per irRECIST**

Complete Response (iCR):	Disappearance of all lesions (whether measurable or not and whether baseline or new) and confirmation by a repeat, consecutive assessment no less than 4 weeks (28 days) from the date first documented is required. Any pathological lymph nodes (whether target or nontarget) must have reduction in short axis to <10 mm.
Partial Response (iPR):	Decrease in tumor burden* \geq 30% relative to baseline. Confirmation by a consecutive assessment at least 4 weeks (28 days) after first documentation required.
Progressive Disease (iPD):	Increase in tumor burden* \geq 20 % and at least 5 mm absolute increase compared to nadir (minimum recorded tumor burden) or qualitative worsening of non-target lesions or a new lesion. For irRECIST, confirmation by a repeat, consecutive assessment no less than 4 weeks (28 days) from the date first documented progressive disease is required.
Stable Disease (iSD):	Neither sufficient shrinkage to qualify for iCR or iPR nor sufficient increase to qualify for iPD.

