Measurable lesions are defined at baseline as lesions that can be accurately measured in at least one dimension (ie, longest diameter for non-nodal lesions and short axis for lymph nodes will be measured and followed) with a minimum size of:

- ≥ 10 mm by CT scan (CT scan slice thickness no greater than 5 mm) or MRI
A lymph node must be ≥ 15 mm in short axis when assessed by CT scan or MRI.

Non-Measurable Lesions:

All other lesions, including small lesions (longest diameter < 10 mm or pathological lymph nodes with ≥ 10 mm but < 15 mm short axis) and other truly non-measurable lesions are considered non-measurable. Examples of non-measurable lesions include some bone lesions, ascites, pleural/pericardial effusion, lymphangitic involvement of the skin or (lymphangitis cutis/pulmonis), cystic lesions, and groups of lesions that are small and numerous.

Documentation of "Target", "Non-Target" and "New" Lesions:

Baseline evaluations will be used to prospectively identify all sites of disease present as close as possible to the enrollment and never greater than or equal to 28 days before the enrollment date. Sites of disease will be characterized as either target, non-target lesions or new lesions.

Baseline Documentation of Target Lesions:

Up to 5 target lesions (a maximum of 2 per organ) will be chosen to measure over the course of therapy (Phase III). Pathological lymph nodes that are defined as measurable must meet the criterion of a short axis of ≥ 15 mm by CT scan in order to be identified as target lesions.

Target lesions should be selected on the basis of their size (lesions with longest diameter) and suitability for accurate repeated measurements by radiographic imaging.

In situations where larger lesions cannot be accurately measured repeatedly (eg, near the diaphragm where respiratory changes may affect measurements), smaller lesions that meet criteria for measurability may be selected instead. Target lesions must not be chosen from a previously irradiated field unless there has been documented tumor progression in that field prior to enrollment. The distribution of the target lesions should be representative of the subject's overall disease (eg, largest lesions per organ).

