A sum of the diameters (longest for non-nodal lesions, short axis for nodal lesions) for all target lesions will be calculated and reported as the baseline sum diameters. The baseline sum of diameters will be used as reference by which to characterize the objective tumor response.

Baseline Documentation of Non-Target Lesions:

Any measurable lesions that were not chosen as target lesions and pathological lymph nodes with short axis ≥ 10 mm but < 15 mm, as well as non-measurable lesions should be identified as non-target lesions. Non-target lesions are evaluated at each timepoint but measurements are not required.

Documentation of New Lesions:

Any new lesion that appears during the course of study will be categorized as a new lesion. New lesions are evaluated at each timepoint but measurements are not required.

Tumor Assessment per RECIST v1.1:

At each subsequent tumor assessment after baseline, the sum of diameters of target lesions (longest for non-nodal lesions and short axis for nodal) will contribute to the total tumor burden.

$$\text{Tumor Burden} = \text{sum of diameter of target lesions}$$

New lesions and non-target lesion measurements are not required and these lesions should be followed qualitatively.

Response Evaluation:

Evaluation of Objective Response:

The subject response will be assessed based on tumor burden (the sum of diameters of target lesions) and qualitative assessment of non-target lesions per the definitions in [Table 15](#).

Table 15. Definition of Tumor Response for RECIST v1.1

Evaluation of Target Lesions	
Complete Response (CR)	Disappearance of all non-nodal target lesions. Any pathological lymph nodes (whether target or non-target) must have reduction in short axis to <10 mm.
Partial Response (PR)	At least a 30% decrease in the sum of diameters of target lesions, taking as reference the baseline sum diameters.
Progressive Disease (PD)	At least a 20% increase in the sum of diameters of target lesions, taking as reference the smallest sum on study (this includes the baseline sum if that is the smallest on study). In addition to the relative increase of 20%, the sum must also demonstrate an absolute increase of at least 5 mm. (Note: the appearance of one or more new lesions is also considered progression)
Stable Disease (SD)	Neither sufficient shrinkage to qualify for PR nor sufficient increase to qualify for PD, taking as reference the smallest sum diameters while on study

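### Criterion 106 tests progression of the irradiated lesion itself, Appendices D and E test progression anywhere in the irradiated field, and neither document says which rule governs the choice of target lesions

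*Protocol*

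**What the plan says.** Three places in the protocol set a rule for target lesions in irradiated tissue.

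- **Section 4.1, criterion 106.** A lesion in a previously irradiated field may not be a target "unless there has been radiographically and/or pathologically documented tumor progression in that lesion prior to enrollment". The test is at lesion level, and the kind of evidence is named.
- **Appendix D, baseline documentation of target lesions** (irRECIST, both phases). The exception applies "unless there has been documented tumor progression in that field prior to enrollment". The test is at field level, and the kind of evidence is not named.
- **Appendix E, same heading** (RECIST v1.1, marked as phase III only). A target may not be "chosen from a previously irradiated field unless there has been documented tumor progression in that field prior to enrollment". This is again a field-level test.

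Appendix D defines "Tumor Burden = sum of diameter of target lesions". In its Table 12, iPR is a fall of at least 30% in that sum from baseline. iPD is a rise of at least 20% over nadir with "at least 5 mm absolute increase compared to nadir (minimum recorded tumor burden) or qualitative worsening of non-target lesions or a new lesion". Phase 1b allows up to 10 targets, 5 per organ.

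SAP Section 6 derives iBOR by reference to Appendix D and BOR by reference to Appendix E, and derives phase 1b modified RECIST BOR in the same way. It adds no rule of its own on irradiated lesions.

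**The concern.** The field rule is the wider one. Every irradiated lesion that meets criterion 106 also meets the appendices. A mass that has not progressed, lying in a field where another lesion has, meets only the appendices. Appendix D is where a site looks when picking targets, and size is one of its selection criteria, so a large residual mass could be chosen.

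Previous irradiation is foreseeable in this population. One entry route is failure of multimodal treatment given with curative intent, and prior radiotherapy is a planned covariate (Protocol 10.1.3, SAP 4.2).

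A mass that does not change adds a constant to the sum of diameters and dilutes percentage change in both directions. The exposed endpoints are the phase 1b irRECIST ones: iORR, iBOR, iDOR, iPFS and, in part, iDCR. The exploratory modified RECIST v1.1 endpoints are exposed in the same way. iORR matters most, because SAP 10.5.2.1 makes it the main efficacy input to the phase 3 decision.

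**Working it through.** No sample size, event count or power in the plan depends on this rule, so there is no planned figure to reproduce. The check has two steps.

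**1. Do the texts give different results from the same scans?** Take an irradiated neck holding one regrown node and one unchanged residual mass.

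- Under criterion 106 the mass is non-target. In Table 14 of Appendix D, a fall of at least 30% in the targets with stable non-target disease and no new lesion is iPR, so the mass does not block response.
- Under the appendix rule taken alone, the mass may be a target and enters the sum.

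The classification can therefore differ.

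**2. By how much?** Let the reference sum be B (baseline for response, nadir for progression), with the stable mass equal to fB and the other targets to (1-f)B. A fractional change c in the other targets changes the sum by c(1-f). Setting this equal to the thresholds gives:

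- iPR: required shrinkage c = 0.30/(1-f)
- target-based iPD: required growth c = 0.20/(1-f), with the 5 mm minimum also met

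The share f is an assumption, shown over a range:

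| f | shrinkage needed for iPR | growth needed for target-based iPD |
|---|---|---|
| 0 | 30% | 20% |
| 0.10 | 33.3% | 22.2% |
| 0.20 | 37.5% | 25.0% |
| 1/3 | 45% | 30% |
| 0.50 | 60% | 40% |
| 0.70 | 100% | 66.7% |

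Above f = 0.70, iPR cannot be reached while the mass stays unchanged.

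**Moderate example (assumed sizes, f = 1/3).** The other targets total 40 mm and the stable mass is 20 mm, with nadir equal to baseline.

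- A 35% shrinkage is -14 mm. Without the mass this is -35%, meeting the iPR threshold. With it, -14/60 = -23.3%, which is iSD.
- A 25% growth is +10 mm. Without the mass this is +25%, meeting the iPD threshold. With it, +10/60 = +16.7%, which is not target-based iPD.

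**Severe example (assumed sizes, f = 0.60).** The node is 20 mm and the mass 30 mm.

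- The node falls to 10 mm: -50% alone, but 40/50 = -20% with the mass.
- The node grows to 26 mm: +30% and +6 mm alone, but 56/50 = +12% with the mass.

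**Scale on iORR.** Protocol 10.2.1 expects about 27 subjects in the efficacy analysis. One reclassified responder is 1/27 = 3.7 percentage points. That holds for any single reclassification and does not estimate how many there are.

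**After the fix.** With the lesion-level rule throughout, such a mass is not a target, so f = 0 and the thresholds return to 30% and 20%.

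**The case against.** The strongest reply is that both texts are prohibitions, so a site obeying both must apply the narrower one, and choosing the residual mass would breach an inclusion criterion. Nothing in the documents shows that any site did so. This stands, and it limits the risk to target selection made from the appendix alone. It does not remove the need for one wording, since no precedence is stated and the SAP points to the looser text.

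Appendix D also asks for lesions that can be measured repeatedly and that represent the overall disease, so size does not decide alone. Allowing up to 10 targets leaves room for such a mass but also reduces its share of the sum. At shares of 10% to 20% the iPR threshold moves only to between 33.3% and 37.5%. These points stand.

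The wording change also comes too late to alter any lesion selection. SAP Section 11 reports that the phase 1b primary analysis has been reviewed and that phase 3 will not proceed. What remains useful is a check on lesions already chosen. That check is post hoc, sits beside investigator-assessed responses, and may need data that the CRF does not hold.

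A reader might infer three stronger things that the documents do not support:

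- **That the field rule lets a subject count as measurable on a barred lesion.** Criterion 106 governs eligibility, and Appendix D's definition of a measurable lesion contains no field rule.
- **That iDCR is inflated generally.** A move from iPR to iSD leaves iDCR unchanged, because SAP Section 6 counts both as disease control. It rises only where iPD becomes iSD.
- **That progression is hidden.** iPD from new lesions, non-target worsening or rapid clinical deterioration is unaffected.

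**Conclusion.** The inconsistency is real and unresolved: a lesion-level test in criterion 106 and a field-level test in Appendices D and E. Where a site relied on the appendix alone, the same scans could be read as iSD rather than iPR, which lowers iORR, and target-based iPD could be delayed. The size follows 0.30/(1-f) and 0.20/(1-f), assuming that the irradiated mass stays unchanged.

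Neither f nor the number of affected subjects is in the documents, so no net effect on iORR can be stated. The documents do not support a claim that the phase 1b result was biased or that the phase 3 decision would have differed. iCR is unaffected, because a persisting mass prevents it whether target or non-target. OS and the DLT endpoint do not use the sum of diameters. With phase 3 cancelled, Appendix E matters only for consistency and for the exploratory phase 1b modified RECIST endpoints.

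**What to change.** 1. **Wording.** In the target-lesion sentence of Appendices D and E, replace the field-level condition with that of criterion 106: "radiographically and/or pathologically documented tumor progression in that lesion prior to enrollment". This settles both the unit (lesion) and the evidence required.

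2. **Check of existing phase 1b data.** For the follow-up and final analyses, where lesion-level radiation and progression history is available, flag target lesions that do not meet criterion 106. Report iORR and iDCR with those lesions treated as non-target, as a labelled post hoc sensitivity analysis beside the investigator-assessed result, which stays primary. State before running it how recorded diameters will be turned into a non-target status, since no qualitative judgement was made for these lesions, and how a subject left with no target lesion is handled. If no lesion is flagged, one sentence in the report closes the point. If the history is incomplete, report how many lesions could not be checked.

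**Cost.** A short text change, a small extra derivation, and possibly some site queries if the CRF does not record radiation history by lesion.
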